7.3 Center Pooling

Given this is a multi-center trial, to account for the pooling of results across sites and regions the following analysis will be performed for primary endpoints of primary cohort, XLV cohort, and bifurcation cohort using complete data:

1. Pooling data of the small sites:
The sites with enrollment of 5 subjects or more are reported individually. The sites with enrollment of 4 or less are pooled into super-sites according to their geographical closeness so that the combined super-sites would have five or more enrolled subjects. If a super-site is with 5 or more subjects, the pooling of this supersite will stop and the pooling of the next super-site will start.
2. Assessment of baseline characteristics across sites:
Important baseline demographic and lesion characteristics (lesion-length, baseline RVD, age, sex, diabetes, history of MI and worst Canadian Cardiovascular Society Angina Class (CCSC)) will be tabulated for each site. Assessment of differences in baseline characteristics across sites will be performed using one-way analysis of variance for continuous parameters and logistic regression for categorical parameters.
3. Analysis on the primary endpoints across sites:
For each primary endpoint, rate of the primary endpoint for every cohort will be presented by site and comparison across sites will be carried out using logistic regression to assess site homogeneity, with the primary endpoint as the dependent variable, and the sites as independent variable. If there is significant difference in baseline characteristics observed in step 2, then this comparison will be adjusted by adding the entire baseline variables listed above into the logistic regression model as additional independent variables.

To account for the pooling of results across regions (US vs. EU), the following analysis will be performed on all three cohorts using complete data:

1. Assessment of homogeneity of baseline characteristics between US and EU:

The two-sample t-test, Fisher's exact test or Cochran-Mantel-Haenszel (CMH) (Modified Ridit scores) will be used depending on the distributions of the baseline covariates. The covariates that will be considered include: lesion-length, baseline RVD, age, sex, diabetes, history of MI and worst Canadian Cardiovascular Society angina class. Statistical non-significance (significance level set at 0.15) for any of the covariates is supportive evidence of the comparability of Resolute arms without adjusting for that covariate. However, any covariate for which the group difference is deemed to be clinically and statistically significant could be adjusted by using propensity scores as discussed below to account for any covariate imbalances.

2. Assessment of Outcome Comparability:

If any of the above baseline covariates is significantly different, then the outcome of primary endpoint between the US and EU will be compared as the following: For each individual a propensity score will be calculated using logistic regression, with indicator for cohort (US, EU) membership as the dependent variable and the above mentioned covariates as the independent variables (covariates will be included regardless of whether or not they are deemed homogenous). Subjects will then be categorized into quintiles based on this propensity score. The 85% confidence interval of propensity score quintile adjusted odds ratio of region will be calculated. If the 85% confidence interval contains one (1), then the US and EU data will be considered poolable.

Statistical non-significance in the primary endpoints for site and region comparisons will confirm that the sites and regions are homogeneous in this trial. Otherwise, the cause of the significant difference will be investigated and further analyses plan will be discussed with FDA.

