5.1 Treatment(s) and Subject Enrollment

The study will be conducted in two geographies, the United States (US) and Europe (EU). Up to 25 US sites (at least 50% of subjects) and up to five EU sites will participate in this study.

At least 510 subjects with ischemic heart disease due to stenotic lesions within coronary arteries that are amenable to treatment with a Resolute Onyx™ 2.0 mm – 5.0 mm stent, meet the eligibility criteria and sign the informed consent form will be included in this study. Subjects may receive treatment of more than one lesion (within a maximum of two target vessels).

The study will have three cohorts with specific and separate analyses (refer to Figure 1). The Primary Cohort will consist of at least 410 subjects who will be treated with at least one 2.0 mm – 4.0 mm diameter Resolute Onyx™ stent. No more than 50 subjects from European sites will be enrolled in the Primary Cohort. A maximum of 41 subjects will be treated with a 2.0 mm Resolute Onyx™ stent.

The Extra Large Vessel (XLV) Cohort will consist of at least 100 subjects who will be treated with at least one 4.5 mm - 5.0 mm diameter stent. Subjects will be enrolled in both the US and EU geographies, with no more than 49 subjects from European sites. Subjects in the XLV Cohort must have at least one lesion amenable to treatment with a 4.5 mm – 5.0 mm stent. Additional lesions may be treated with any available Resolute Onyx™ size stent but these subjects will be designated as a participant in the XLV Cohort as the primary analyses will be based on 4.5 and 5.0 mm stents.

The Bifurcation Cohort will consist of at least 200 subjects of which approximately 15 eligible subjects are expected to be included for analysis from the Primary and XLV cohorts, with an addition of approximately 185 subjects recruited specifically for the Bifurcation Cohort. Subjects will be treated with the full stent size matrix, 2.0 mm – 5.0 mm stents. Subjects will be enrolled in both the US and EU geographies, with no more than 99 subjects from European sites included in the analysis.

RESOLUTE ONYX Post-Approval Study Statistical Analysis Plan

10 October, 2021

Revision 7.0

Page 19 of 32

Form
Medtronic

The study will be conducted to allow data collection and analysis for a minimum of 36 months from treatment of the final subject or until the study has been formally terminated. Health status assessments will be completed at 30 days and 6, 12, 24, and 36 months post-procedure.

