6.1 Primary Cohort

If the 12-month TLF rate of the Resolute Onyx stent™ is shown to be significantly less than 17.5%, then the Primary Cohort will be considered to have met its primary endpoint. In other words, the null and the alternative hypotheses are:

$$H_0: P_{TLF} \geq 17.5\%$$

$$H_1: P_{TLF} < 17.5\%$$

where P_{TLF} is the true primary endpoint rate for the study stent. Rejection of the null hypothesis will signify that the PG is met.

Assuming a one-sided alpha level of 0.05 and a true event rate of 11.3%, an effective sample size of 369 subjects will yield 96% power to reject the null hypothesis. Assuming a 10% loss to follow-up rate, a total sample size of 410 RESOLUTE ONYX Post-Approval Study subjects will be enrolled in the Primary Cohort. An expected event rate of 7.95% was derived from both arms of the RESOLUTE All-Comers (RAC) trial (excluding unprotected left main (UPLM) and PCI of 3 vessels). Modification of 3.31% was added to the expected rate to adjust the difference in MI reporting per third UDMI. This resulted in the expected event rate of 11.3%. The performance goal 17.5% is a 55% extension from the expected event rate of 11.3%.

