6.3 Bifurcation Cohort

If the 12-month TVF rate is shown to be significantly less than 24.5% for the RESOLUTE ONYX Bifurcation Cohort, then the Bifurcation Cohort will be considered to have met its primary endpoint. Therefore, the null and the alternative hypotheses are:

$$H_0: P_{TVF} \geq 24.5\%;$$

$$H_a: P_{TVF} < 24.5\%$$

where P_{TVF} is the true primary endpoint rate for the study stent. Rejection of the null hypothesis will signify that the PG is met. This PG is based on review of clinical evidence from published literature.

Assuming a one-side alpha level of 0.05 and a true event rate of 16.3%, an effective sample size of 180 subjects will yield 85% power to reject the null hypothesis. Assuming 10% loss to follow-up rate, a total sample size of 200 subjects will be needed; hence data on a total of 200 subjects will be generated.

The expected rate for the RESOLUTE ONYX Bifurcation Cohort was obtained by utilizing the weighted average of outcomes from the RESOLUTE All-Comers (RAC) study in patients with single bifurcations treated with single or double stents (excluding unprotected left main lesions and patients with three vessel disease), and the from the provisional stenting arm of the TRYTON study. The weighted average is shown in Table 1. Then the expected rate of 12-month TVF was modified upwards by 3.3% in order to account for the utilization of Third UDMI definition. Therefore, the expected rate of 12-month TVF is 16.3%.

Table 1: Expected 12-month TVF rate for the RESOLUTE ONYX Bifurcation Cohort

Study/Arm	Stent Used	N	12m TVF Rate
RAC (Resolute Arm) - single bifurcation treatment	ZES	133	11.60%
RAC (Xience V Arm) - single bifurcation treatment	EES	136	12.20%
TRYTON – Provisional Stenting Arm*	DES	339	13.9%**
Weighted Average			13.00%
* Data from TRYTON SSED			
**Adjusted downwards from 15.3% to 13.9% to account for the difference in true versus non-true bifurcated lesions per Medina Classification that were treated in the Resolute All comer study and the provisional stenting arm of the TRYTON study			

7. Statistical Methods

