7.9 Evaluation of Objectives

7.9.1 Analysis of the Primary Endpoints

7.9.1.1 Primary Cohort

The primary endpoint is Target Lesion Failure (TLF, defined as cardiac death, target vessel myocardial infarction (Q wave and non-Q wave), or clinically-driven target lesion revascularization by percutaneous or surgical methods) at 12 months.

It is estimated that in average the TLF rate at 12 months post procedure is 11.3%. The performance goal (PG) is set to be 17.5%, which is approximately 55% above the expected TLF rate for Resolute Onyx.

If the 12 months TLF rate of the Resolute Onyx Post-Approval Study is shown to be significantly less than the PG, then the trial will be considered to have met its objective. In other words, the assessment of TLF at 12 months is a testing with the following null and alternative hypotheses:

$$H_0: p \geq 17.5\% \text{ vs. } H_1: p < 17.5\%,$$

where p is the true Onyx 12 months TLF rate.

The assessment of the null hypothesis will be carried out at the one-sided 0.05 level of significance. Rejection of the null hypothesis indicates the Onyx 12 months TLF rate is significantly below 17.5%.

The count and percentage of subjects with 12-month TLF will be presented. A one-sided upper 95% confidence interval of the Resolute Onyx stent 12-month TLF rate will be calculated through binomial (exact) method. If this upper limit is below 17.5%, the clinical objective will be considered to have been met. All ITT subjects in primary cohort with evaluable value will be included in the primary analysis.

As a supplementary analysis, to account for missing data, subjects who drop out prior to 330 days post-procedure and do not experience TLF will have their 12-month TLF-missing status ("yes"/"no") imputed using the multiple imputation and tipping point analysis.

The multiple imputation approach will use SAS V9 PROC MI. The covariates to be used in the imputation model are lesion-length, baseline RVD, age, sex, diabetes, history of MI, Canadian Cardiovascular Society Angina Class, and TLF status at visits prior to dropout. One hundred imputed data sets will be generated. An overall TLF rate and its one-sided upper 95% confidence intervals will be generated across the one hundred imputed data sets. For the subjects with 2 or more target lesions, the longest lesion length and the smallest baseline RVD will be used in the imputation model.

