7.9.1.3 Bifurcation Cohort

The count and percentage of subjects with 12-month TVF will be provided. A one-sided upper bound of the 95% CI of the observed 12-month TVF rate will be calculated through binomial (exact) method. If this upper limit of the 95% CI is below 24.5%, the clinical objective will be considered to have been met for the Bifurcation Cohort.

As a supplementary analysis, to account for missing data, subjects who drop out prior to 330 days post-procedure and do not experience TVF will have their 12-month TVF-missing status ("yes"/"no") imputed using the multiple imputation and tipping point analysis.

The multiple imputation approach will use SAS V9 PROC MI. The covariates to be used in the imputation model are lesion-length, baseline RVD, age, sex, diabetes, history of MI, Canadian Cardiovascular Society Angina Class, and TVF status at visits prior to dropout. One hundred imputed data sets will be generated. An overall TVF rate and its one-sided upper 95% confidence intervals will be generated across the one hundred imputed data sets. For the subjects with 2 or more target lesions, the longest lesion length and the smallest baseline RVD will be used in the imputation model.

The tipping point analysis will impute the most 12-month TVF-missing status as “yes” so that the one-side upper 95% confidence interval will be less than or equal to the performance goal of 24.5%. For all the three cohorts, the analysis of the primary endpoint will be repeated for PP set as a secondary analysis.

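### SAP 7.3 reads a non-significant site or region comparison as confirming homogeneity, which those comparisons cannot show, especially for moderate US-EU differences and for spread between sites

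*SAP*

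**What the plan says.** SAP 7.3 sets out two checks on the primary endpoint of each cohort.

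- **Sites.** Sites with four or fewer subjects are merged into super-sites of at least five. The endpoint rate is shown by site, and sites are compared by logistic regression. Neither the test statistic nor the significance level is given.
- **Regions.** Baseline covariates are compared between US and EU at the 0.15 level. If any differs, a propensity-quintile-adjusted odds ratio is calculated: "If the 85% confidence interval contains one (1), then the US and EU data will be considered poolable". No outcome comparison is written for the case where no covariate differs.

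The section then concludes: "Statistical non-significance in the primary endpoints for site and region comparisons will confirm that the sites and regions are homogeneous in this trial". Only a significant result leads to investigation and discussion with FDA. For the baseline covariates, the same section uses milder language and treats non-significance as support for comparability.

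SAP 5.1 limits the European share: "No more than 50 subjects from European sites will be enrolled in the Primary Cohort". The corresponding limits are 49 in the XLV Cohort (at least 100 subjects) and 99 in the Bifurcation Cohort (at least 200). Up to 25 US and five EU sites take part.

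**The concern.** A non-significant comparison is compatible with equal rates, and also with any difference the data were too sparse to detect. The SAP's sentence does not separate the two. In the Primary Cohort the European arm is small, in XLV both arms are small, and with up to 30 sites many sites would have no event at all.

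The study report could therefore state that homogeneity was confirmed when the data hardly bear on the question. That statement would stand beside a pooled rate judged against a performance goal, and a non-significant result would end the inquiry. If no covariate happens to differ, the region conclusion would rest on an outcome comparison that the SAP does not specify.

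**Working it through.** **1. The plan's own figures.** The SAP gives power only for the tests against the goals. Success requires the exact one-sided 95% upper bound to lie below the goal.

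- Primary ("Assuming a one-sided alpha level of 0.05 and a true event rate of 11.3%, an effective sample size of 369 subjects will yield 96% power"): with n = 369 and a goal of 17.5%, success means at most 52 events. P(X ≤ 52 | 369, 0.113) = 95.9%, against 96% stated.
- Bifurcation ("Assuming a one-side alpha level of 0.05 and a true event rate of 16.3%, an effective sample size of 180 subjects will yield 85% power"): with n = 180 and a goal of 24.5%, success means at most 34 events. P(X ≤ 34 | 180, 0.163) = 85.1%, against 85% stated.
- Loss to follow-up: 369/0.9 = 410 and 180/0.9 = 200.

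The design inputs reproduce, so they are used below.

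**2. Region comparison: inputs.** Evaluable subjects are the caps less 10%.

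- Primary: EU 50 × 0.9 = 45; US 360 × 0.9 = 324.
- XLV: EU 49 × 0.9 ≈ 44; US 51 × 0.9 ≈ 46.
- Bifurcation: EU 99 × 0.9 ≈ 89; US 101 × 0.9 ≈ 91.

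Event rates are 11.3% (Primary) and 16.3% (Bifurcation). The documents give no XLV rate, so 11.3% is assumed.

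**3. Region comparison: rule.** The 85% interval is log OR ± 1.44 × SE, with SE² the sum of the reciprocals of the four cell counts. Regions are called poolable if it contains zero. I enumerated all pairs of binomial outcomes, without propensity adjustment. In each range below, one end holds the US rate at the planned value and the other holds the cohort average there.

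| True EU rate / US rate | Primary | XLV | Bifurcation |
|---|---|---|---|
| 1 (equal) | 86% | 86% | 85% |
| 1.5 | 63-64% | 74-77% | 53-60% |
| 2 | 29-34% | 51-62% | 13-29% |
| 3 | 2-5% | 12-39% | at most 5% |
| 0.5 | 62-65% | 63-70% | 29-41% |

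Entries are the percentage of trials called poolable.

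A hand check for Primary, doubling, US rate fixed:

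- Rates are 11.3% and 22.6%, so log OR = −1.231 − (−2.061) = 0.830.
- SE = √[1/(45 × 0.226 × 0.774) + 1/(324 × 0.113 × 0.887)] = √(0.127 + 0.031) = 0.397.
- Power ≈ Φ(0.830/0.397 − 1.44) = Φ(0.65) ≈ 74%, so about 26% missed. Exact enumeration gives 29%.

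**4. Precision when the regions are equal.** SE = √[(1/n_US + 1/n_EU)/(p(1 − p))] = 0.502, 0.666 and 0.404. The typical 85% interval for the odds ratio, exp(±1.44 × SE), is 0.49-2.06 (Primary), 0.38-2.61 (XLV) and 0.56-1.79 (Bifurcation). Even a perfectly null result would not exclude differences of this size.

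**5. Site comparison.** I assumed equal sites: 30 of 12 (Primary), 30 of 6 (Bifurcation) and 15 of 6 (XLV).

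- Expected events per site: 12 × 0.113 = 1.4; 6 × 0.163 = 1.0; 6 × 0.113 = 0.7.
- Share of sites with no event if all sites are equal: 0.887¹² = 24%; 0.837⁶ = 34%; 0.887⁶ = 49%.

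Site rates were then drawn with a logit SD of 0.5, the median site having the planned rate. For Primary, the 10th to 90th percentile of site rates is about 6% to 19%. Percentage of simulated trials rejecting at 0.05:

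| Test | Primary | Bifurcation | XLV |
|---|---|---|---|
| Pearson | 28% | 16% | 9% |
| Likelihood ratio | 47% | 34% | 11% |

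Holding the mean site rate at the planned value instead lowers these by at most about four points. When sites are truly equal, the likelihood-ratio test rejects in about 12-13% of Primary and Bifurcation trials at nominal 0.05, so part of its apparent power is inflated error. Raising alpha to 0.15 takes the Pearson figures to about 47-49%, 33-34% and 21-22%. The answer therefore depends on choices that the SAP leaves open.

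**The case against.** The best defence is that the region rule is deliberately sensitive. An 85% interval corresponds to a two-sided 0.15 level, and a doubling of the European rate would be found more often than not in the two cohorts with a formal hypothesis. This stands. A reader might infer that large US-EU differences would usually be missed; for Primary and Bifurcation the figures do not support that, since a tripling is missed in at most about 5%. The weakness lies in moderate differences, in XLV and in the site comparison.

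A reader might also infer that the site test has almost no power as specified. That follows only from a Wald test, which breaks down when sites have no events. The SAP says only logistic regression, and other tests do better. The supported criticism is that the test and its level are missing.

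The region percentages are not literal forecasts. European numbers are caps rather than targets, the odds ratio would be adjusted, and the comparison is conditional on a covariate difference. They also depend on which rate is held fixed. With the Bifurcation US rate fixed, a doubling gives a pooled rate of (91 × 16.3% + 89 × 32.6%)/180 = 24.4%, almost at the goal, so the trial would usually fail anyway.

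Finally, the reader is not left blind. Rates by site will be shown, an interval for the region odds ratio is produced when that comparison runs, and SAP 7.4 requires the number analysed. These points soften the consequence, but they do not make the concluding sentence correct.

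**Conclusion.** The concern holds. Followed exactly, SAP 7.3 yields a statement of confirmed homogeneity that its comparisons cannot support. A European rate 1.5 times the US rate would pass as poolable in more than half of trials in every cohort, and a doubling would pass in roughly one in eight to six in ten, depending on cohort and on the rate held fixed. A between-site logit SD of 0.5 would go undetected in more than half of trials in every cohort with either test at 0.05.

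These sizes assume European enrolment at the caps, 10% loss, unadjusted odds ratios, 11.3% for XLV, and equal site sizes and numbers as stated. Fewer European subjects would generally reduce power: with 23 evaluable in Primary, a doubling (cohort average fixed) is detected in about 51-53%.

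A reader might go further and infer that the primary conclusions are compromised. The documents do not support that. Success in the Primary Cohort is decided by "If this upper limit is below 17.5%, the clinical objective will be considered to have been met", the Bifurcation rule has the same form at 24.5%, and neither depends on the outcome of SAP 7.3. Their type I error is unchanged. What is at stake is the homogeneity statement and whether investigation and discussion with FDA are triggered. The change should be made, but it does not threaten the design.

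**What to change.** In SAP 7.3:

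1. Replace the conclusion that homogeneity is confirmed with: *no evidence of a difference was detected; differences up to the confidence limit are not excluded*, with the limit stated.
2. Run the US-EU comparison of the primary endpoint in every cohort, whatever the covariate results. Report the US rate, the EU rate and their difference with a confidence interval beside the pooled rate.
3. Report the between-site SD with its interval for each primary endpoint.
4. Name the site test and its alpha, choosing one whose error rate holds with about one event per site.

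The cost is SAP wording and one more table. No new data and no change to design or sample size are needed. The downside is that the stated conclusion becomes slightly less favourable.

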7.4 Handling of Missing, Unused, and Spurious Data and Dropouts

Every effort will be undertaken to minimize missing data. In time-to-event outcomes, drop-outs will be censored at the time of discontinuation, consistent with the Kaplan-Meier approach. Unless otherwise specified, no statistical techniques will be used to impute missing data for continuous or categorical characteristics and outcomes. The number of subjects included in each analysis will be reported so that the reader can assess the potential impact of missing data.

Screening and acceptance testing of these data will be carried out in accordance with Data Management Plan. To this end, all data involved in the determination of endpoints will be screened for missing and unusual values. Any missing data that affect the ability to determine or analyze any endpoint will be queried by Data Management for confirmation of irretrievability. Unusual values, such as outliers, will also be queried, and if confirmed, will be used as recorded.

